10.3 General plan of statistical analysis

10.3.1. General principles of statistical analysis

Statistical analysis is performed by a qualified biostatistician. It includes:

- description of patients included in the study;
- the number of patients dropped out of the study;
- the number of AE/AR, SAE;
- analysis of initial homogeneity;
- efficiency analysis;
- tolerability and safety analysis;
- $-- {\rm statistical\ conclusions}.$

10.3.2. Analysis of the initial state/base-line state of the group

Analyze the group according to clinical and demographic parameters at the time of inclusion in the study. Use methods of descriptive statistics to describe the initial state/base-line state in groups (for quantitative parameters - n, arithmetic mean, median, standard deviation, minimum and maximum value; for categorical parameters - number and share in %).

10.3.3. Analysis of effectiveness

Additional information about the statistical model for evaluating the effectiveness of the drug by the main variable is given in Section 10.1. "The content of statistical analysis".

A) The primary outcome of efficiency – Proportion (%) of patients with response (R).

Primary efficiency variable – achievement of R during the study. *R is defined according to criteria* *:

| Bioven | Page 71 |
|----------------------------|--------------------------------|
| Trial Code: 2021-BV-ITP-BP | Version 1.4 from July 03, 2023 |

- Patients with R: the number of platelets > $30x10^{9}/l$ and at least a two-fold increase from the baseline count. This must be confirmed by at least 2 blood tests performed once every 7 days and the absence of bleeding;

The categories of the variable will be defined as "Yes" or "No" respectively.

* The criteria are defined according to the Guideline on the clinical investigation of human normal immunoglobulin for intravenous administration (IVIg), EMA/CHMP/BPWP/94033/2007 rev. 4, 16 December 2021 as well as according to the criteria of the international working group on ITP in 2009. (Rodeghiero, F., Stasi, R., Gernsheimer, T., Michel, M., Provan, D., Arnold, D. M., ... & George, J. N. (2009). Standardization of terminology, definitions, and outcome criteria in immune thrombocytopenic purpura of adults and children: report from an international working group. Blood, The Journal of the American Society of Hematology, 113(11), 2386-2393.);

B) Secondary effectiveness variables.

For variables assessed once at the final visit, descriptive statistics methods will be used to describe these variables (for quantitative parameters - n, arithmetic mean, median, standard deviation, minimum and maximum value; for categorical parameters - number and share in %). 95% confidence intervals will be calculated. In the case of measuring variables at more than two visits, one-way analysis of variance (ANOVA) methods will be used.

Censored data will be analyzed using the Kaplan-Meier method or the log-rank test.

Secondary efficacy endpoints are transformed into corresponding efficacy variables:

Achieving a complete response (CR) during the study.

CR is determined according to the criteria *:

 Patients with CR: platelets count > 100 x 10⁹/L, which is confirmed by 2 blood tests performed at least 7 days apart and the absence of bleeding;

The categories of the variable will be defined as "Yes" or "No" respectively.

The variable is analyzed for patients who achieved a response (R) during the study.

Non-response (NR) during the study.

NR is determined according to the criteria *:

- Patients with NR: $patient count < 30 \times 10^{9}$ /L or less than two-fold increase of baseline platelet count. This must be confirmed by at least 2 blood tests performed approximately 1 day apart, or the presence of bleeding;

The categories of the variable will be defined as "Yes" or "No" respectively.

The variable is analyzed relative to the total number of patients included in the analysis.

Loss of response (loss of R).

R loss is determined according to the criteria *:

 Patients with loss R: a decrease platelet count < 30 x 10⁹/L or less than two-fold increase of baseline platelet count, or the occurrence of bleeding. Platelet counts confirmed at least 2 blood tests performed approximately 1 day apart.

The categories of the variable will be defined as "Yes" or "No" respectively.

The variable is analyzed for patients who achieved a response (R) during the study.

Loss of complete response (loss of CR).

CR loss is determined according to the criteria *:

Patients with loss of CR: decrease platelet count $< 100 \times 10^9$ /L, or the occurrence of bleeding. Platelet counts confirmed at least 2 blood tests performed approximately 1 day apart.

The categories of the variable will be defined as "Yes" or "No" respectively. The variable is analyzed for patients who achieved a complete response (CR) during the study.

Time (in days) from treatment start to onset of a response (R);

A Kaplan Meier curve will be constructed and the median time to event will be estimated. The variable is analyzed for patients who achieved a response (R) during the study.

Time (in days) from treatment start to onset of a complete response (CR);

A Kaplan Meier curve will be constructed and the median time to event will be estimated. The variable is analyzed for patients who achieved a complete response (CR) during the study.

Duration (in days) of response (R);

A Kaplan Meier curve will be constructed and the median time to event will be estimated. The variable is analyzed for patients who achieved a response (R) during the study.

Duration (in days) of complete response (CR);

A Kaplan Meier curve will be constructed and the median time to event will be estimated. The variable is analyzed for patients who achieved a complete response (CR) during the study.

C) Quantitative variables of efficiency, which are measured at study entry (T $_{start}$) and at the final visit (T $_{endpoint}$).

Provide indicators of descriptive statistics (n, arithmetic mean, median, standard deviation, minimum and maximum value) for time points T start and T endpoint, and also for differences [T endpoint – T start]. Represent this dynamic graphically.

Calculate for these parameters their relative change in comparison with the initial state/base-line according to the formula:

$$X(\%) = \frac{T endpoint - T start}{T start} * 100,$$

Evaluate the dynamics using the Student's paired test or the Wilcoxon signed rank test, depending on the results of testing the normality of the distribution of differences $[T_{endpoint} - T_{start}]$ using the Shapiro-Wilk test.

D) Evaluation of quantitative variables measured at more than two measurement points.

Specify the indicators of descriptive statistics (n, arithmetic mean, median, standard deviation, minimum and maximum value) for each measurement point, as well as for the differences $[T_i - T_{start}]$, where *i* are subsequent visits. Build a dynamics graph.

Calculate for these parameters their relative change at each subsequent visit in comparison with the initial state according to the formula:

$$X(\%) = \frac{Ti - Tstart}{Tstart} * 100,$$

where *i* is subsequent visits according to the patient examination scheme.

Evaluate the dynamics of changes in quantitative variables using univariate analysis of variance (ANOVA) or rank analysis depending on the normality of the distribution, which is tested using the Shapiro-Wilk test. At the same time, the dependent variable is the analyzed parameter, the "visit" factor is a fixed parameter. To assess the magnitude and significance of the difference between visits using contrast analysis (simple contrasts) or post hoc analysis using Tukey's test (for ANOVA) or Wilcoxon signed rank test with Holm's correction (for rank test). To verify the prerequisites for the application of variance analysis, a check of the normality of the distribution of residuals will be
| Bioven | Page 73 |
|----------------------------|--------------------------------|
| Trial Code: 2021-BV-ITP-BP | Version 1.4 from July 03, 2023 |

performed using the Shapiro-Wilk test. In the event that the balances are not normally distributed, an appropriate rank analysis will be performed. Make statistical conclusions.

triate substear conclusions.

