| Inclusion criteria: Signed Patient Informed Consent Form for participation Men and women aged 18-65; Confirmed primary chronic ITP (lasting > 12 months) A full blood count should be normal except for the issue with low hemoglobin levels (but above 90 g/L) may be of bleeding: | on in the study; since diagnosis); olated thrombocytopenia. Patients be included if there are symptoms |
| If bleeding symptoms are diagnosed, the reticulocyte - Platelet count <30 x 10⁹ /L; If the patient is taking corticosteroids, the treatment r least 2 weeks prior to screening); Negative pregnancy test (for women of child-bearing | count should be measured; regimen/dose should be stable (at potential); |

| Bioven |
|----------------------------|
| Trial Code: 2021-BV-ITP-BP |

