According to the literature, the effectiveness of IVIG when used in patients with ITP ranges from 60-80% [Anurag Singh, Günalp Uzun, Tamam Bakchoul / Primary Immune Thrombocytopenia: Novel Insights into Pathophysiology and Disease Management // J. Clin. Med. 2021, 10, 789. https://doi.org/10.3390/jcm10040789]. [Godeau B., Caulier M-T. Decuypere L. et al. Intravenous immunoglobulin for adults with autoimmune thrombocytopenic purpura: results of a randomized trial comparing 0'5 and 1 g/kg b.w. // British Journal of Hematology, 1999, 107, 716-719; Rugayyah J. Almizrag, Donald R. Branch Efficacy and mechanism of intravenous immunoglobulin treatment for immune thrombocytopenia in adults // Ann Blood 2021;6:2 http://dx.doi.org/10.21037/aob-20-87; Drew Provan, Roberto Stasi, Adrian C. Newland et al. International consensus report on the investigation and management of primary immune thrombocytopenia // Blood, 14. - Jan 2010, Vol. 115, Number 2]). However, the most similar in performance evaluation standards and study design is the 2020 publication [Parodi E, Russo G, Farruggia P, Notarangelo LD, Giraudo MT, Nardi M, et al. Management strategies for newly diagnosed immune thrombocytopenia in Italian AIEOP Centers: do we overtreat? Data from a multicenter, prospective cohort study. Blood transfusion. 2020;18(5):396.1, which indicates the effectiveness of IVIG in the treatment of ITP - 78% (the drug administration scheme recommended by the EMA and this Protocol, the total number of patients in the group is 82). According to our data and data from the literature, immunoglobulin belongs to drugs with a highly variable efficacy of 20-25%. Therefore, we consider it expedient to set the limit of the difference in efficacy δ between the obtained and expected results for non-inferiority research at -25%.

Thus, for a significance level of 5% and a statistical power of 80%, the effectiveness of the comparison drug reaches 78%, the limit of the difference in fractions (difference in effectiveness) without clinical significance δ is -0.25. Then the calculation of the minimum sample size will look like this:

 $n = (1,96+1,28)2 \times (0,78 \times (1-0,78) / (0,78 - 0,78+0,25)^2 = 29$

Taking into account the risk (20%) of dropping out of patients for various reasons, 36 patients will be included in the study.

Methods of statistical analysis that will be used:

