3. PURPOSE AND OBJECTIVES OF RESEARCH

Objective: To evaluate the efficacy, safety and tolerability of Bioven in patients with chronic primary immune thrombocytopenia, with evidence of non-inferiority compared to the literature data regarding the level of effectiveness of existing IVIG products.

Tasks of study:

- To evaluate the proportion (%) of patients who achieved the response (R) during the study, platelet count> 30x10⁹ / 1 and at least double their initial number, as confirmed by at least 2 blood tests performed every 7 days; absence of bleeding) during therapy with the studied drug Bioven.
- To evaluate the effeciency of the studied drug Bioven in comparison with the literature data
- To evaluate the presence and severity of hemorrhagic syndrome as a result, which is included within 4 weeks after starting therapy;
- To evaluate the proportion (%) of patients who achieved a complete response (CR) during the study (platelet count> 100 x 10^9 / l, confirmed by at least 2 blood tests performed every 7 days; no bleeding) during treatment with the study drug Bioven.
- To evaluate the proportion (%) of patients who did not respond (NR) during the study with a platelet count $<30 \times 10^9$ / L or less than a 2-fold increase in platelet count from baseline. This must be confirmed by at least 2 blood tests with a difference of one day, or the presence of bleeding during therapy with the study drug Bioven.
- To evaluate the proportion (%) of patients who lost the response (R) during the study (a decrease in platelet count (<30 x 10^9 / L, or less than twice the initial or bleeding. Platelet counts should be confirmed at least twice with an interval of 1 day).
- To evaluate the proportion (%) of patients who lost a complete response (CR) during the study, a decrease in platelet count, $<100 \times 10^9$ / l, or the occurrence of bleeding. Platelet counts should be confirmed at least twice with an interval of 1 day).
- To determine the time from the start of treatment with the study drug Bioven to the onset of the response (R);
- To determine the time from the start of treatment with the studied drug Bioven to the onset of a complete response (CR);
- To set the duration of the response (R);
- To set the duration of the complete response (CR);
- To evaluate the frequency and severity of possible adverse events/adverse reactions (AE/AR).

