8 EVALUATION OF EFFICIENCY

8.1 Primary efficacy endpoint:

Part (percent) of patients with response (R).

R is determined according to the following criteria:

- Patients with R: platelets count $> 30x10^{9}/L$ and at least a two-fold increase from the baseline count. This must be confirmed by at least 2 blood tests at least 7 days apart, and the absence of bleeding;

The primary efficacy variable is achievement of R during the study (yes/no).

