8.2 Secondary efficiency endpoints

Part (percent) of patients with a complete response (CR).

CR is determined according to the following criteria:

- Patients with CR: platelets count > 100 x 10^{9} /L, which is confirmed by 2 blood tests performed at least 7 days apart and the absence of bleeding;

Part (percent) of patients with no response (NR).

NR is determined according to the following criteria:

- Patients with NR: platelet count $< 30 \times 10^{9}$ /L or less than two-fold increase of baseline platelet count. This must be confirmed by at least 2 blood tests performed approximately 1 day apart, or the presence of bleeding;

Part (percent) of patients with loss of response (loss of R).

Loss R is determined according to the following criteria:

- Patients with loss R: a decrease platelet count < 30×10^9 /L or less than two-fold increase of baseline platelet count, or the occurrence of bleeding. Platelet counts confirmed at least 2 blood tests performed approximately 1 day apart.

Part (percent) of patients with loss of complete response (loss of CR).

CR loss is determined according to the following criteria:

- Patients with loss of CR: decrease platelet count < 100 x $10^9/L$, or the occurrence of bleeding. Platelet counts confirmed at least 2 blood tests performed approximately 1 day apart.

Time (in days) from treatment start to onset of a response (R); Time (in days) from treatment start to onset of a complete response (CR); Duration (in days) of response (R); Duration (in days) of complete response (CR);

Secondary efficacy endpoints are transformed into corresponding efficacy variables

Safety

- Frequency (percent) of adverse events

- Frequency (percent) of serious adverse events

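### Complete response is defined as a percentage of patients but analysed among responders only, which inflates the reported rate by 1/(response rate)

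*Combined protocol and SAP*

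**What the plan says.** Section 8.2, like the synopsis, lists the endpoint as "Part (percent) of patients with a complete response (CR"). The matching objective in section 3 is "To evaluate the proportion (%) of patients who achieved a complete response (CR) during the study". None of these three places limits the percentage to patients who responded.

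Section 10.3.3, part B, defines CR as a yes/no variable and then adds: "The variable is analyzed for patients who achieved a response (R) during the study". The same sentence recurs later in 10.3.3 for loss of R, time to R and duration of R. The occurrence at issue is the first one, between the CR categories and the start of the NR definition, so it belongs to CR.

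For NR, the next variable in the list, the rule is different: "The variable is analyzed relative to the total number of patients included in the analysis". No section specifies a CR analysis on all patients.

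**The concern.** CR is an outcome that any treated patient can reach or fail to reach, as are R and NR. Following 10.3.3 as written would produce a percentage of responders for an endpoint labelled as a percentage of patients. CR would then stand on a different base from NR in the same results table.

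Three things are at stake:

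- **Overstatement.** A reader who takes the endpoint at its name will read the figure as a share of treated patients, and it will be too high.
- **Comparability.** The synopsis and section 10.3.7 say in general terms that results will be set against published data. A rate among responders cannot be set beside a rate among treated patients. In a single-arm study there is no control group with the same denominator to offset the inflation.
- **Direction.** The denominator is itself a treatment outcome. For a fixed number of complete responses, fewer responders give a higher reported CR percentage.

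**Working it through.** **The plan's own figure.** The documents state no CR rate. The only computed figure nearby is the sample size for R, and it reproduces: (1.96 + 1.28)² × 0.78 × 0.22 / 0.25² = 28.82, rounded up to 29. It does not involve CR, so the CR denominator leaves it unchanged.

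**Inputs**

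- Entry criterion (synopsis; also 5.1): "Platelet count <30 x 10⁹ /L".
- R (8.1): platelets above 30 x 10⁹/L and "at least a two-fold increase from the baseline count", confirmed by at least two tests at least 7 days apart, without bleeding.
- CR (8.2 and 10.3.3): platelets above 100 x 10⁹/L, "which is confirmed by 2 blood tests" at least 7 days apart, without bleeding.
- Planning response rate (synopsis, sample size): "the effectiveness of the comparison drug reaches 78" per cent. The literature range cited there is 60-80%.

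**Step 1: is every CR an R?** With a baseline below 30, a count above 100 exceeds the threshold of 30. It is also more than a 100/30 = 3.3-fold rise, so the two-fold condition is met. The confirmation interval and the bleeding condition are the same in 8.1 and 8.2. CR is therefore a subset of R.

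**Step 2: the inflation factor.** Let N be the patients analysed, r the responders and c the complete responders.

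(c/r) / (c/N) = N/r = 1/(response rate)

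- Response 60%: 1/0.60 = 1.67
- Response 78%: 1/0.78 = 1.28
- Response 80%: 1/0.80 = 1.25

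**Step 3: what would be reported.** The CR rates in the first column are assumptions, because the documents give none.

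| CR among all patients (assumed) | Reported at R = 60% | Reported at R = 78% | Reported at R = 80% |
|---|---|---|---|
| 30% | 50% | 38% | 38% |
| 40% | 67% | 51% | 50% |
| 50% | 83% | 64% | 63% |

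**Step 4: the same in counts.** Responders are 78% of N, rounded. The CR counts are assumed at about 40% of N, and the intervals are exact 95% intervals. The three values of N are the minimum sample size, the number after the dropout allowance, and the enrolment stated in section 4.1.

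| N | Responders | CR | CR / all patients | CR / responders |
|---|---|---|---|---|
| 29 | 23 | 12 | 41.4% (23.5-61.1) | 52.2% (30.6-73.2) |
| 36 | 28 | 14 | 38.9% (23.1-56.5) | 50.0% (30.6-69.4) |
| 40 | 31 | 16 | 40.0% (24.9-56.7) | 51.6% (33.1-69.8) |

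At these sizes the change of denominator moves the estimate by 11 to 12 percentage points.

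**The case against.** The strongest reply is that section 8.2 uses the same percent-of-patients wording for loss of R and loss of CR. Section 10.3.3 analyses those among responders and complete responders, and nobody would object. On that reading the phrase fixes no denominator, and 10.3.3 is simply where denominators are assigned. This stands in part: the phrase alone does not settle the matter. But only a patient who has responded can lose a response, so conditioning is built into the loss endpoints. It is not built into CR. The explicit all-patient rule for NR, the next variable, is the firmer evidence.

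Other limits also stand:

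- The formal non-inferiority comparison uses R only. The documents give no literature CR rate and plan no specific CR comparison, so the comparability concern rests on their general statement about literature data.
- CR among responders, labelled as such, is a valid conditional proportion. The all-patient rate follows by division if both counts are reported.
- CR comes first among the secondary endpoints by list order only. No hierarchy or test is attached to it.
- Section 10.3.3 states an all-patient denominator only for NR. For R it states none, although nothing there restricts R.

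These points limit the weight. They do not remove the mismatch between the endpoint as named and the rule for computing it.

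**Conclusion.** The concern holds. As written, 10.3.3 yields a CR percentage that is too high for the endpoint named in the synopsis and sections 3 and 8.2. The factor is exactly 1/(response rate): 1.28 at 78%, and between 1.25 and 1.67 over the cited range.

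The exact factor rests on two readings. Baseline is taken as the qualifying count below 30 x 10⁹/L; the visit schedule lists no platelet count between screening and the first infusion. The 7-day confirmation for R in 10.3.3, which is worded slightly differently from 8.1, is taken as the same rule. The CR rates of 30-50% are illustrative.

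The consequence is confined to one descriptive secondary endpoint. It should be corrected before analysis, because in an open-label study the denominator should not remain open to choice once the data are visible.

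**What to change.** In 10.3.3, replace the sentence after the CR definition with one stating that CR is analysed relative to the total number of patients in the efficacy analysis, with its 95% confidence interval. Add the same statement for R, so that R, CR and NR share one explicit denominator. If CR among responders is of interest, keep it as a separate line labelled supplementary and show both counts. Leave the responder-based denominators for loss and duration of response as they are.

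Which analysis set supplies the total (section 10.4 names the per-protocol set for efficacy) is a separate question that this change does not settle.

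The cost is a sentence or two of text. No extra patients, visits or data are needed. The headline CR figure will be lower.
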